7.9.3 Longitudinal Outcome Data

Quality of life and functional status secondary endpoints will be measured longitudinally by patient self-report through the portal or call center. Missing data may occur with missed contacts, participant withdrawal, or refusal to answer questions. The mixed model approach planned for analysis of these endpoints yields unbiased inference in the presence of a missing at random (MAR) missingness mechanism, meaning that the distribution of missing data is the same as that of non-missing data, conditional on observed covariates. As part of planned secondary analyses following the primary final report, we will examine patterns of missingness and characterize participants by missingness pattern and treatment group to assess plausibility of the MAR assumption. If concerns are noted, then a pattern mixture model approach will be considered. If there are no concerns regarding the MAR assumption, but there is significant missing data (more than 10% of participants with more than two missed measures), an inverse probability weighting approach will be considered.

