7.7 Secondary Endpoints

Secondary endpoints include:

- All cause death
- Hospitalization for nonfatal MI
- Hospitalization for nonfatal stroke
- Coronary revascularization (PCI or CABG)
- Quality of life and functional status components include:
 - o Current Health
 - Physical function
 - Depression
 - Fatigue
 - Sleep disturbance
 - Social roles and activities
 - Pain Interference

Patient reported coronary revascularization events that do not match to one of the electronic sources will not be further verified. As such, these PROs will not be counted as events in the secondary event analyses.

All-cause death will be analyzed using a Cox proportional hazards model. All other time-to-event outcomes will be analyzed using the Fine and Gray method, equivalent to the Cox proportional-hazards model when competing risks are present, with all-cause death as the competing risk. The test will be two-tailed and will be performed at an overall α of 0.05. The proportional hazards assumption will be checked for randomized treatment arm using weighted Schoenfeld residuals. If there is evidence of non-proportionality, a cautious interpretation of the model hazard ratio will be encouraged, and non-parametric event rate estimates will be emphasized, as described for the primary effectiveness analysis.

Quality of life and functional status data are collected on numerical scales (1:excellent health-5:worst health). They will be analyzed as continuous variables. Mixed models using restricted maximum likelihood estimation (REML) will be employed to model trajectory of measures over time by treatment group. Mixed models account for the correlation structure imposed by repeated measures within participants while using all available data, from baseline to the end of the study, regardless of exact follow-up time. The intercept and slope will be modeled as random effects. The covariance structure for random effects will be modeled using an unstructured form. Time from baseline measurement and randomized treatment arm will be included in the model as fixed effect. Time will be tested for linearity using natural cubic splines. An interaction between randomized treatment arm and time will be assessed, as will the overall effect of randomized treatment arm.

Since these measures are discrete scores, it is expected that normality assumptions will not hold. Natural log and other appropriate transformations will be considered, as well as several distributions and link functions.

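### SAP 7.9.3 makes the only not-at-random analysis of the patient-reported outcomes depend on a review of observed data, which cannot separate MAR from MNAR; pre-specify that analysis unconditionally

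*SAP*

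**What the plan says.** SAP 7.7 analyses each quality-of-life and functional-status item with a mixed model. On the fixed part: "Time from baseline measurement and randomized treatment arm will be included in the model as fixed effect", with the arm-by-time interaction also assessed. On the random part: "The intercept and slope will be modeled as random effects". No baseline characteristics are listed.

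SAP 7.9.3 names the sources of missing scores: "Missing data may occur with missed contacts, participant withdrawal, or refusal to answer questions". It states that the mixed model "yields unbiased inference in the presence of a missing at random (MAR) missingness mechanism", and it glosses that condition in this way: "the distribution of missing data is the same as that of non-missing data, conditional on observed covariates".

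The check comes later, once the main results have been reported: "we will examine patterns of missingness and characterize participants by missingness pattern and treatment group to assess plausibility of the MAR assumption". Two branches follow:

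- "If concerns are noted, then a pattern mixture model approach will be considered".
- If there are no such concerns but missingness is substantial ("more than 10% of participants with more than two missed measures"), inverse probability weighting is considered.

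The SAP does not say which characteristics are compared or what counts as a concern.

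**The concern.** MAR allows missingness to depend on what was observed but not, given that, on the unseen score. Everything in the planned review is observed. The review is therefore asked a question that its data cannot answer, and the answer decides whether an MNAR analysis is considered. If it is not, the fallback is a method that usually rests on the same MAR assumption.

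The trial is open-label, and these scores come only from the participants themselves, through the portal or the call center. If willingness to answer depends on how a participant currently feels, and does so differently by dose, the mixed model can show a dose difference that is not there or hide a real one. The report could then state that no concern about MAR was found.

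**Working it through.** The documents give no figure for this check, so there is none to reproduce. All simulation settings below are assumptions, and the contrast between scenarios matters more than any single size.

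**1. What the review can see.** Write R for the missingness pattern, Y(obs) and Y(mis) for the seen and unseen scores, and X for the covariates. MAR says P(R | Y(obs), Y(mis), X) = P(R | Y(obs), X). Pattern tables describe X and Y(obs) by R and arm. A difference there is evidence against data missing completely at random (MCAR), but not against MAR. The distribution of Y(mis) given Y(obs), X and R is what separates MAR from MNAR, and it is not in the data.

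**2. One follow-up score.** Settings: 15,000 participants, no dose effect, baseline to follow-up correlation 0.6, about 25% missing, baseline-adjusted comparison. Three checks at 5% each: baseline score by missingness, missing rate by arm, and the arm-by-missingness difference in baseline. The chance of at least one flag with nothing to find is about 1 − 0.95³ = 14%. In the MNAR rows the dependence is in one arm only.

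| Missingness driven by | Log-odds per SD | Any flag | Bias (SD) | Type I error |
|---|---|---|---|---|
| Baseline score (MAR) | 0.1 | 100% | 0.000 | 5.5% |
| Part of unseen score unrelated to baseline | 0.1 / 0.2 / 0.3 | 13.5 / 16.2 / 17.2% | −0.019 / −0.039 / −0.061 | 21.8 / 73.0 / 98.0% |
| Actual change from baseline | 0.1 / 0.2 / 0.3 | 44 / 89 / 99% | see below | – |
| Unseen score itself | 0.1 / 0.2 / 0.3 | 54 / 98 / 100% | see below | – |

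The first two rows use 600 trials per cell and the last two 300. A separate run of the second row with 300 trials gave 14 / 14 / 19%.

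The biases can be checked by hand. With missing fraction p, log-odds β per SD of the residual and residual SD σ = √(1 − 0.6²) = 0.8, the mean residual among those observed is about −pβσ. For β = 0.1, 0.2, 0.3 this gives −0.25 × β × 0.8 = −0.02, −0.04, −0.06. The standard error is 0.8 × √(2/5,625) = 0.015, with 7,500 × 0.75 = 5,625 observed per arm. At β = 0.2 the ratio 0.04/0.015 is about 2.65, so rejection is about Φ(2.65 − 1.96) = 75%, close to the simulated 73%.

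The last two rows are also biased. Per SD of the driver, change (−0.4 × baseline + residual, SD √(0.16 + 0.64) = 0.894) at 0.2 puts 0.2 × 0.8/0.894 = 0.179 on the residual, so bias is about −0.25 × 0.179 × 0.8 = −0.036. The unseen score puts 0.2 × 0.8 = 0.16 on it, so bias is about −0.032.

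**3. The SAP's model form.** Random intercept and slope; fixed time, arm and arm-by-time; fitted by maximum likelihood (the SAP plans REML). Settings: 2,000 participants, eight six-monthly follow-ups, SDs 0.7 (intercept), 0.15 per year (slope) and 0.6 (residual), true slope difference 0, 30 replicates. In B to E the dependence runs in opposite directions in the two arms, which is deliberately strong. A flag means that, within an arm, baseline score or a baseline covariate differs between participants with more than two missed measures and the rest (Bonferroni over four tests).

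| Scenario | Bias in slope difference | Coverage | Flagged |
|---|---|---|---|
| A. MCAR | −0.002 | 87% (26/30) | 0% |
| B. MAR, last observed score | −0.004 (Monte Carlo SE 0.003) | 93% | 100% |
| C. MNAR, current unseen deviation only | −0.133 | 0% | 0% |
| D. MNAR, current unseen score | −0.129 | 0% | 100% |
| E. MAR given a baseline covariate outside the model and related to slope | −0.148 | 0% | 100% |

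The valid cases (A, B) are flagged 0% and 100%; the biased cases (C, D, E) 0%, 100% and 100%. The review separates A and C from B, D and E. It does not separate valid from biased.

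**4. Other cover in the documents.** Protocol III.F.8 assigns multiple imputation to analyses other than the primary, with no not-at-random offset stated. Its pattern-mixture analysis with separate offsets by dose is for event-free survival. The tipping-point analyses in SAP 7.9.2 and 7.10 concern time-to-event endpoints. None supplies an MNAR analysis of the patient-reported scores.

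**The case against.** The strongest reply is that the review is useful and often raises the alarm when it should. Much of this stands.

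- A reader might infer that the check simply tests MCAR, so that it alarms when the mixed model is valid and stays silent when it is biased. That is too strong. MNAR that correlates with earlier scores leaves traces: the change and unseen-score rows and scenario D are mostly flagged. The near-chance rate belongs to the special case where missingness depends only on the part of the score unrelated to what was observed.
- A reader might also infer that a pattern difference is harmless because it is compatible with MAR. The planned model does not support that. It has only time and arm as fixed effects, so a predictor of missingness outside the model that also relates to trajectory causes real bias (scenario E), and the pattern tables are what would reveal it.
- SAP 7.9 also plans to collect reasons for missing data and to describe baseline characteristics and clinical events by availability of follow-up and by arm. That informs a judgement of plausibility better than the few comparisons simulated here. It is still observed data.
- The SAP speaks of assessing plausibility and of considering a model. It sets no test and no binding rule.
- The biases in step 2 are small. The type I errors of 73% and 98% reflect 15,000 participants, not a large distortion.

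What the reply does not answer is that a flag from D looks like a flag from B, and silence from C looks like silence from A. Judgement based on these tables cannot tell when the MNAR analysis is needed.

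**Conclusion.** The point holds in a limited form. The condition in SAP 7.9.3 is not informative about MAR versus MNAR, has no stated criterion, and leads only to a method being considered. It can flag a valid analysis (about 100% of simulated trials, no bias) and can miss a biased one (about 14–17% flagged, near chance, bias 0.02–0.06 SD). It does not always miss MNAR, and a flag can signal real bias.

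The flag rates and bias sizes rest on assumed correlation, missing fraction and strength of dependence. Step 2 uses one follow-up score instead of the SAP's mixed model. Step 3 uses that model form, but with strong opposing dependence by arm and only 30 replicates. The conclusion that observed data cannot decide the question does not depend on these settings.

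The effect is confined to secondary endpoints, for which the SAP makes no multiplicity adjustment. Nothing here bears on the primary effectiveness or safety result. The change is worth making but is not critical. SAP 7.9.2 offers a precedent: its tipping-point analysis for the primary endpoint is triggered by the amount of withdrawal (more than 5%), not by a review of MAR, and its inflation factors differ by arm.

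**What to change.** In SAP 7.9.3, remove the condition and pre-specify one delta-adjusted (pattern-mixture) sensitivity analysis for each patient-reported domain, run in all cases:

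- Impute scores missing while the participant is alive, under MAR and by arm, with observed earlier scores and baseline predictors of missingness in the imputation model. The predictors are needed for cases like E; a delta alone does not deal with them.
- Shift the imputed scores by a separate delta in each arm over a stated grid, for example 0 to 0.5 SD worse, and report where the dose conclusion changes. At a single visit with the same missing fraction p in both arms, the dose difference moves by about p × (difference in deltas). With p = 25%, a difference of 0.16 SD moves it by 0.04 SD.
- Keep the pattern tables, to describe missingness and to choose the imputation predictors.

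The cost is SAP wording, modest programming on data already collected, and one supportive table per domain. The missingness review is already scheduled after the primary final report, so the primary analysis is not delayed.

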7.10 Planned Sensitivity Analyses

Sensitivity analyses will be conducted to assess robustness of trial conclusions to 1) nonadherence to randomized aspirin dose and 2) under-reporting and misclassification of endpoint data. Sensitivity analyses will be focused on primary analysis of the primary efficacy and safety endpoints, but the methods may be generalized to key secondary endpoints. **Non-adherence**. A sensitivity analysis will be conducted in the ITT population in which participant-reported aspirin dose is added to the primary analysis Cox model as a time-varying covariate.

COVID-19. A sensitivity analysis will be conducted in the ITT population in which censoring for the primary efficacy endpoint will occur on December 31, 2019 the original study end date and prior to COVID entering the United States. Although we do not expect a differential impact of randomized aspirin dose, COVID-19 could drastically increase the observed primary efficacy endpoint.

Bayesian Analysis. As part of planned secondary analyses following the primary final report, a sensitivity analysis for the primary efficacy endpoint will be performed using a Bayesian proportional hazards model or a Bayesian piece-wise exponential non-proportional hazards model, pending assessment of the proportional hazards assumption. Using the Bayesian posterior distribution, we will calculate the posterior probability that the unknown treatment specific hazard ratio exceeds thresholds of 1.0, 1.05, 1.10, 1.15 and 1.20 and reciprocals of those numbers. Because Bayesian inferences may be sensitive to the choice of prior distribution, further sensitivity analyses will be performed and reported for a range of possible prior distributions.

Proportional hazards assumption holds.

Bayesian analysis requires the specification of a prior probability distribution representing prior information about the set of unknown model parameters before observing the study data. Because prior information about the treatment effect is limited, we will pre-specify a flat (uniform) prior for the Cox model regression coefficient. The selection of a uniform prior reflects the subjective assessment that prior information about the direction and magnitude of the treatment effect is neutral. It also allows posterior inferences to be dominated by the current study data as opposed to the prior.

Bayesian estimation of the Cox model will be based on the method of Kalbfleisch (1978) which uses the Cox partial likelihood function in place of the full data likelihood. Using the Cox partial likelihood is advantageous because it lends itself to efficient Bayesian MCMC computation via Gibbs sampling and avoids the requirement to specify a prior distribution for the baseline hazard function. Using the partial likelihood in place of the full likelihood has been justified on the grounds that it closely approximates a Bayesian analysis of the full data likelihood when the prior distribution for the baseline hazard function is a highly diffuse gamma process prior (Sinha, Singh, Ibrahim, 2003).

Posterior means and other summaries of the posterior distribution will be calculated using Markov Chain Monte Carlo (MCMC) simulations as implemented in the SAS PHREG procedure. To reduce Monte Carlo error and ensure convergence, we will generate 50,000 sets of simulated parameter values after an initial burn-in period of 2,000 iterations.

Proportional hazards assumption is violated.

The piece-wise exponential model lends itself to simple and efficient Bayesian MCMC computation, allowing the model to be flexible enough to accommodate a variety of shapes for the unknown treatment-specific hazard function. To implement this approach, follow-up time will be divided into discrete time intervals. The treatment-specific hazard function for the primary endpoint will be approximated as a constant function within each treatment group and time interval. A summary measure of treatment effect will then be computed by estimating the ratio of

the cumulative average hazard ratio over follow-up. The cumulative average hazard ratio reduces to the hazard ratio statistic when the proportional hazards assumption holds, but does not rely on the PH assumption for its validity or interpretability. A flat prior will be chosen for all model parameters requiring a prior distribution.

Under-reporting and misclassification of endpoints. The primary and key secondary endpoints are derived from multiple sources reflecting varying levels of data completeness and sensitivity/specificity of electronic phenotype definitions for true diagnosis. It is therefore critical to clarify the assumptions underlying inference around the treatment effect and perform sensitivity analyses to assess robustness of this inference to potential violations of the assumptions.

For the primary analysis (and related secondary analyses), we make the following assumptions:

- Death is reported without error.
- Other components of the primary endpoint may be subject to under-reporting and misclassification but these errors are non-differential, i.e. probability of an error is consistent across randomized treatment groups.
- Patient self-report with confirmation is assumed to have nearly perfect specificity since incorrect self-reports will be excluded by examination of medical record. There may be some under-reporting since identification of the event depends on self-report. Some selfreported events may not be confirmed or contradicted if participant did not consent to confirmation process.
- CDM endpoints may be under-reported since participants may be treated for events outside the CDM health systems or events within the health system may be missed. Misclassification may occur due to imperfect electronic phenotype definitions.
- Claims data (CMS and private) is assumed to be complete for enrolled participants and changes in enrollment status are independent of trial outcome. Misclassification may occur due to imperfect electronic phenotype definitions.

We will perform two sets of sensitivity analyses: 1) to assess impact of under-reporting on the primary analysis and 2) to assess impact of misclassification on the primary analysis. Because available data sources vary across participants, we summarize the potential for error due to under-reporting and misclassification according to each potential combination of available data. To simplify classification of participants, we will not attempt to account for changes in data sources over time, but rather classify participants according to data sources available for more than half of follow-up time.

	Data sources available			Potential error		
Scenario	Self- report	Out of Network Confirmation	CDM	Claims (CMS or private)	Under- reporting	Misclassification
1	Х				Yes	Yes
2	Х	Х			Yes	No
3	х		Х		Yes	Yes
4	Х			Х	No	Yes
5	Х		Х	Х	No	Yes
6			Х		Yes	Yes
7				Х	No	Yes

8		Х	Х	No	Yes
9*				Yes	No

*Only information is vital status check at end of trial.

To assess impact of under-reporting due to participants moving or seeking care outside of the CDM health system, we will repeat the primary analysis modifying the censoring rules for CDM data such that the censoring date will be the last date the patient encountered the health system. This will include inpatient and outpatient visits, labs, vitals and prescription medication fills. All other censoring dates will remain the same.

Under the assumption that under-reporting is non-differential between treatment groups, the impact on primary analysis inference would be a loss of power. If the primary result is non-significant then we will assess overall impact of under-reporting, by performing a tipping point analysis to identify how many events would have to be missed to achieve significance. We will take an approach that is adapted and simplified from that described by Little et al (2016) for a sensitivity analysis for missing data. A Weibull model of the primary endpoint will be fit to the entire ITT population, with independent variables including an indicator that participant is at risk for under-reporting (Scenarios 1, 2, 3 and 6 in the table) and selected baseline characteristics. Other independent variables may be considered. Events will be sequentially added for those participants at risk of under-reporting across treatment groups. For each increment, *i* events will be imputed from the Weibull model 1000 times. A Cox model as specified for the primary analysis will be fit to the resulting dataset and treatment effect hazard ratio will be estimated, with standard errors adjusted using standard multiple imputation combining rules. The increment will be increased until the upper limit of the 95% CI for the HR of the treatment effect crosses 1.0.

To assess impact of misclassification of electronic phenotype definitions, we will repeat the primary analysis modifying the code-based definitions of primary endpoints to include codes in 1) principal position only and 2) any position.

To further assess impact of misclassification, we will perform a tipping point analysis expanding on methods developed by Liublinska and Rubin (2014) for missing data in clinical trials. Positive predictive value and negative predictive value will be varied from 0 to 1 to reclassify events or non-events for those participants at risk of misclassification (Scenarios 1 and 3-8). For each combination of PPV and NPV, the corresponding number of reclassified events will be imputed 1000 times. Reclassified events will randomly selected and set to non-events. Reclassified non-events will be generated from the Weibull model described in tipping analysis for under-reporting. A Cox model as specified for the primary analysis will be fit to the resulting dataset and treatment effect hazard ratio will be estimated, with standard errors adjusted using standard multiple imputation combining rules. A 95% confidence interval will be calculated for the HR of the treatment effect. Resulting inference based on comparing confidence limits to 1.0 will be presented in a heat map with positive predictive value and negative predictive value reported on the x- and y-axes. Note that this analysis does not relax the assumption of consistency of misclassification across treatment groups.

